### 2.3 Secondary Objectives:

- To determine the reduction of pleural opacity (in percentage) on chest radiograph from day 1 (randomization) to day 7
- To determine the change on inflammatory markers (WBC/CRP) from day 1 (randomization) to day 7
- To determine the outcome :
  - Length of hospital stay (in days) after randomization for each group
  - The need of surgical intervention in 30 days
  - Adverse effects following t-PA/DNase and pleural irrigation
  - Mortality rate at 30 days

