#### 3.3 Sample size and Power of Study

By using power and sample size programme calculator :

Prior data indicate that the failure rate among controls is 0.15. If the true failure rate for experimental subjects is 0.32, we will need to study 39 experimental subjects and 39 control subjects to be able to reject the null hypothesis that the failure rates for experimental and control subjects are equal with

probability (power) 0.8. The Type I error probability associated with this test of this null hypothesis is 0.5. We will use a continuity-corrected chi-squared statistic or Fisher's exact test to evaluate this null hypothesis.

N = 39+/-4 (IPFT with alteplase and DNase) and 39+/-4 (pleural irrigation with normal saline)

Study used as a reference :

Pleural irrigation trial (PIT): a randomised controlled trial of pleural irrigation with normal saline versus standard care in patients with pleural infection Clare E. Hooper, Anthony J. Edey, Anthony Wallis, Amelia O. Clive, Anna Morley, Paul White, Andrew R.L. Medford, John E. Harvey, Mike Darby, Natalie Zahan-Evans and Nick A. Maskell,

Reference for sample size taken from the primary outcome of this research in which patients receiving saline irrigation had a significantly greater reduction in pleural collection volume on computed tomography compared to those receiving standard care (median (interquartile range) 32.3% (19.6–43.7%) reduction versus 15.3% (–5.5–28%) reduction) (  $p < 0.04$ ).

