### Medication Regimen :

t-PA (Alteplase) 5mg and DNase (Pulmozyme)5mg

t-PA (Alteplase) that is available in our pharmacy is 50mg ampoule and DNase (Pulmozyme) is 2.5mg per ampoule

The number of installation of intrapleural t-PA/DNase depends on the discretion of the treating physician (at least 6 hours apart between each dose). 5mg of Alteplase (t-PA) and 5mg DNase are diluted in each 50ml of 0.9% sodium chloride solution. t-PA and DNase are not mixed together in one syringe. The detailed method of t-PA/DNase therapy administration is described in Appendix 1. In brief, both medication are administered sequentially which t-PA is first instilled intrapleurally and the chest tube is then clamped for 45 minutes, then unclamped to allow free drainage for 45 minutes. The same procedure is then repeated for DNase. Selection of the timing of treatment and removal of chest tube are depending on the chest physician's judgement.

However, as for patients who were randomized into pleural irrigation group, subjects were administered 250 ml of 0.9% sodium chloride via chest tube a three way tap from a drip stand which were allowed drainage freely over 1 hour. Pleural irrigation will be performed minimum of 3 installations and maximum of 9 installation (3 times per day).

Both groups received standard care of treatment : which includes regular flushing of chest drain to maintain patency using 20mls of normal saline.

The primary outcome was to evaluate the volume of pleural effusion drainage (in mls) 72 hours following randomization. The volume drained measured after subtracting the amount of volume administered as per protocol.

The secondary outcome are measured by the change in the area of pleural opacity in chest x-ray (day 7 post t-PA/DNase compared to baseline), measured as the percentage of the ipsilateral hemithorax occupied by effusion. The area of pleural opacity and the area of the ipsilateral hemithorax will be measured digitally by two radiologists using Horos Project Software, v3.2.1 as described previously in Multicentre Intrapleural Sepsis Trial 2 (MIST-2)

Other outcomes that will be monitored include :

1. Inflammatory markers including serum C-reactive protein (CRP) & white blood count
2. Length of hospital stay in days
3. The need of surgical intervention within 30 days
4. Adverse effects :
  - a. Chest pain required escalation of analgesics
  - b. Systemic bleeding
  - c. Pleural bleeding

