### 3.7 Study protocol /flow chart

### 3.7 Statistical Analysis

Statistical analysis will be performed using the available SPSS software version 19. All numerical data will be subjected to normality testing using Shapiro-Wilk test. All normally distributed data will be expressed as mean  $\pm$  standard deviation (SD) whereas non-normally distributed data were expressed as median (IQR). For normally distributed data, parametric test with Student's t-test will be used. For non-normally distributed data, the Mann-Whitney test will be used or equivalent nonparametric tests. Within groups, the Wilcoxon rank sum test will be used. For qualitative data, Chi-Square test and Fisher's Exact test will be used. The significant p-value will be taken as  $<0.05$  or in the case of multiple comparisons it will be adjusted with a Bonferonni correction.

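### The significance rule does not say which tests the Bonferroni correction covers, so the threshold for the primary outcome cannot be derived from the plan

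*Combined protocol and SAP*

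**What the plan says.** The whole multiplicity plan is the last sentence of section 3.7 Statistical Analysis. The threshold is p below 0.05, or "in the case of multiple comparisons it will be adjusted with a Bonferonni correction". The sentence is complete as printed, and no other section defines a family of tests, a number of tests or an order of testing.

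The outcomes to which it could apply are spread over several places:

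- **Primary.** Drained volume in ml, at 48 hours in section 2.2 and at 72 hours in section 3.6 (Medication Regimen).
- **Secondary (section 2.3).** Chest-radiograph opacity, length of stay, surgery within 30 days, 30-day mortality, and two laboratory markers: "To determine the change on inflammatory markers (WBC/CRP) from day 1 (randomization) to day 7". Adverse effects stand in the same list.
- **Adverse effects.** Section 3.6 has three items under "Other outcomes that will be monitored include". The monitoring tables in the same section have eight rows.
- **Repeated measurements.** The monitoring tables schedule white cell count on days 0 to 3 and day 7, and drained volume at baseline and days 1 to 3. Section 3.7 also plans within-group tests.

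Section 3.7 assigns chi-square or Fisher's exact tests to all qualitative data. That takes in surgery, mortality and the adverse effects.

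**The concern.** A reader who has the primary p-value in hand cannot tell from the plan whether it is significant. A primary p of 0.02, for example, passes at 0.05 and fails at every level that spreads the correction over the listed outcomes. The trial is open-label, and nothing in the text stops the choice of reading from being made after results are seen.

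Each reading has its own cost. If the primary is corrected along with everything else, it loses power to tests that do not bear on the main claim. If nothing is corrected, several secondary outcomes are each tested at 0.05, although section 2.4 states directional hypotheses for inflammatory parameters, length of stay and surgical referral as well as for drainage. If adverse effects are inside the correction, the bar for declaring an excess of bleeding or chest pain rises, which is the wrong direction for a safety comparison.

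**Working it through.** **The plan's own figure.** Section 3.3 gives a sample size but no multiplicity figure. Its inputs are: "Prior data indicate that the failure rate among controls is 0.15"; "If the true failure rate for experimental subjects is 0.32"; "probability (power) 0.8"; and "The Type I error probability associated with this test of this null hypothesis is 0.5". It states a null hypothesis of equality, which I read as two-sided. With δ = 0.17 and mean rate 0.235:

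- n = [z(α/2)·√(2·0.235·0.765) + z(power)·√(0.15·0.85 + 0.32·0.68)]² / 0.17².
- At α = 0.5: (0.6745·0.5996 + 0.8416·0.5874)² / 0.0289 = 28.0. The continuity correction, n/4·[1 + √(1 + 4/(nδ))]², gives 38.8, so 39 per arm. This is the stated figure.
- At α = 0.05 the same inputs need 97 per arm, or 108 with the continuity correction. With 39 per arm the power at two-sided 0.05 is about 42% (uncorrected test).

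So 39 per arm does not give 80% power at 0.05 even for the binary rates used. That is a separate problem. It matters here because the 80% starting point below is an illustration and not this trial's power.

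**Possible thresholds for the primary.** The Bonferroni level is 0.05/k, with k counted from sections 2.2, 2.3 and 3.6.

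| Tests corrected together | k | Level for the primary |
|---|---|---|
| None, or only repeated or within-group comparisons | 1 | 0.05 |
| Primary + opacity, WBC, CRP, stay, surgery, mortality | 7 | 0.0071 |
| The same + 3 adverse effects in the outcome list | 10 | 0.0050 |
| The 7 + 8 adverse-effect rows of the monitoring table | 15 | 0.0033 |

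One of the eight rows is treatment-related death, which overlaps with mortality. Counting it once gives k = 14 and 0.05/14 = 0.0036.

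**Power kept, for illustration.** For a test with 80% power at two-sided 0.05, power at 0.05/k is Φ(1.960 + 0.842 − z), where z is the two-sided critical value at 0.05/k.

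- k = 7: Φ(2.802 − 2.690) = 0.54
- k = 10: Φ(2.802 − 2.807) = 0.50
- k = 15: Φ(2.802 − 2.935) = 0.45

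None of these is this trial's power for drained volume. The documents give no difference and no SD in ml.

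**No correction at all.** Six independent secondary tests at 0.05 give 1 − 0.95⁶ = 0.26 for at least one false positive. Leaving mortality out, five give 1 − 0.95⁵ = 0.23. Independence is an assumption. These outcomes are plausibly correlated, which would usually make the true figure lower.

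**Adverse effects.** Assume 39 per arm and no events in one arm. The two-sided Fisher p for x v 0 is then 2·C(39,x)/C(78,x).

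| Events | p |
|---|---|
| 5 v 0 | 0.0546 |
| 6 v 0 | 0.0254 |
| 7 v 0 | 0.0116 |
| 8 v 0 | 0.0052 |
| 9 v 0 | 0.0023 |

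The smallest excess that reaches significance is therefore:

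- at 0.05: 6 v 0 (6/39 = 15%);
- at 0.05/8 = 0.00625, a family of the eight adverse-effect rows alone: 8 v 0 (21%);
- at 0.05/15 = 0.0033, the all-tests family: 9 v 0 (23%).

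**The case against.** The best defence is that the clause is conditional and has an ordinary use in a two-arm trial. White cell count and drained volume are measured on several days, and section 3.7 mentions within-group tests shortly before the Bonferroni clause. On that reading the correction applies to repeated comparisons and a single named primary stays at 0.05. This is a natural reading and it may be the intended one. The text does not say so, however, and it excludes the wider reading no more than the narrow one. It also does not settle how the six secondary outcomes are to be treated.

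Two stronger inferences are tempting, and the documents do not support them.

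- **That the primary will be judged at about 0.003.** That figure is not in the plan. It is one end of a range that I constructed by counting tests. The five hypotheses of section 2.4, for example, would give 0.05/5 = 0.01.
- **That the plan hides harm.** It nowhere says that adverse effects will be corrected; it only fails to exempt them. They are monitored and recorded by day whatever the p-value, so a correction would make a harm harder to declare significant and would not conceal it.

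It is also fair to say that testing secondary outcomes only after a significant primary is a design choice, and its absence is not an error. The preference for Holm is better founded. It controls the same family-wise error as Bonferroni and never rejects fewer hypotheses.

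**Conclusion.** The point stands as an ambiguity with consequences: the primary outcome's threshold may be 0.05, or anywhere from 0.0071 down to 0.0033 on the counts above, and the plan does not decide. The illustrative loss from 80% power to between 54% and 45% depends on an assumed starting power that section 3.3 does not deliver at 0.05. The adverse-effect figures depend on 39 per arm, zero events in one arm, and adverse effects being corrected at all, which the plan leaves open.

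The two time points for the primary are a further route to multiplicity. Naming one threshold does not help while 48 and 72 hours both stand. The change is worth making before any comparison by arm.

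**What to change.** Reconcile the 48 h time point of section 2.2 with the 72 h time point of section 3.6, then replace the last sentence of section 3.7 with wording to this effect:

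1. The single primary outcome, drained volume at the one stated time point, is compared between arms at two-sided 0.05 without adjustment.
2. The between-arm tests of opacity, WBC, CRP, length of stay and surgery form one family of five, controlled at 0.05 by Holm's method instead of plain Bonferroni. The ordered p-values are compared in turn with 0.05/5 = 0.0100, 0.05/4 = 0.0125, 0.05/3 = 0.0167, 0.05/2 = 0.0250 and 0.05, stopping at the first failure.
3. Adverse effects and mortality are reported by arm as counts and risk differences with unadjusted 95% confidence intervals, and stand outside the multiplicity correction.

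A rule that secondary claims require a significant primary may be added but is optional. If daily or within-group comparisons are kept, state whether they are descriptive or corrected, and over how many tests. The cost is one paragraph of wording, with no extra patients or data.

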## 2.4 Study Hypothesis

1. Subjects in the IPFT has more volume of pleural fluid drainage compared with pleural irrigation group
2. Subjects in the IPFT has greater reduction of inflammatory parameters compared with pleural irrigation group
3. Subjects in the IPFT has shorter length of hospital stay compared with pleural irrigation group
4. Subjects in the IPFT has less surgical referral rate compared pleural irrigation group
5. There is no difference of mortality rate between both groups

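### Optional improvement: Holm's step-down procedure could replace the Bonferroni correction at the same 5% family-wise error and would never reject less, though the documents do not fix the size of the gain

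*Combined protocol and SAP*

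**What the plan says.** Section 3.7 Statistical Analysis fixes the level with "The significant p-value will be taken as" below 0.05 and adds that "in the case of multiple comparisons it will be adjusted with a Bonferonni correction". No stepwise method is mentioned, so the ordinary reading is single-step Bonferroni: with m tests in the family, each is compared with 0.05/m. The section does not say which comparisons form the family, how many there are, or whether the primary outcome is one of them.

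Section 2.3 lists the secondary outcomes: opacity, WBC and CRP, length of stay, surgery, adverse effects and mortality. That is seven if WBC and CRP are counted separately. Section 2.4 predicts several benefits of IPFT at once, among them "Subjects in the IPFT has greater reduction of inflammatory parameters compared with pleural irrigation group" and "Subjects in the IPFT has shorter length of hospital stay compared with pleural irrigation group", and also fewer surgical referrals. For mortality it predicts no difference.

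**The concern.** Single-step Bonferroni keeps every test at 0.05/m even after other hypotheses in the family have been rejected. Holm relaxes the threshold after each rejection: 0.05/m for the smallest p-value, 0.05/(m-1) for the next, and so on, stopping at the first failure. If several of the sponsor's predictions are true together, Bonferroni will call some real differences non-significant that Holm would have declared at the same family-wise error. At stake are second and later findings within a family, most naturally the secondary outcomes. Arms of 39 leave little power to spare.

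**Working it through.** **The plan's own figure.** Section 3.3 gives failure rates of 0.15 and 0.32, "probability (power) 0.8", and states: "The Type I error probability associated with this test of this null hypothesis is 0.5". With mean rate 0.235 and difference 0.17:

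- Uncorrected n = [z(alpha/2) x sqrt(2 x 0.235 x 0.765) + 0.8416 x sqrt(0.15 x 0.85 + 0.32 x 0.68)]^2 / 0.17^2.
- At the printed alpha of 0.5, z = 0.6745: (0.4044 + 0.4944)^2 / 0.0289 = 27.96.
- Continuity correction: (27.96/4) x [1 + sqrt(1 + 4/(27.96 x 0.17))]^2 = 38.8, so 39 per arm. This reproduces the plan.

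The 39 therefore contains no allowance for multiplicity, and changing the correction method alters no stated figure.

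**Why Holm gives the same protection.** Suppose m0 of the m null hypotheses are true. When Holm first rejects a true one, at most m - m0 hypotheses have gone before it, so its threshold is at most 0.05/m0. The chance that any of the m0 true nulls falls below 0.05/m0 is at most m0 x 0.05/m0 = 0.05, whatever the dependence between outcomes. Every Holm threshold is at least 0.05/m, so nothing Bonferroni rejects is lost. Both methods compare the smallest p-value with 0.05/m, so the chance of at least one rejection is identical.

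**Thresholds for m = 5.** Bonferroni: 0.01 for all. Holm: 0.01, 0.0125, 0.0167, 0.025, 0.05.

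**Size of the gain.** Assumed, because the documents do not say: a family of five (opacity, CRP, WBC, length of stay, surgery), normal test statistics, correlation 0.3, two-sided 0.05. From the plan: 39 per arm. A standardised difference d gives a test statistic with mean d x sqrt(39/2) = 4.416d. Average Bonferroni power is then approximately Phi(4.416d - 2.576):

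- d = 0.4: Phi(-0.81) = 21%
- d = 0.5: Phi(-0.37) = 36%
- d = 0.65: Phi(0.29) = 62%

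Holm has no such simple formula and was simulated, with 400,000 trials per scenario.

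| Real effects (of 5) | d | Bonferroni, average power | Holm, average power |
|---|---|---|---|
| 5 | 0.4 | 21% | 25% |
| 5 | 0.5 | 36% | 43% |
| 5 | 0.65 | 62% | 72% |
| 3 | 0.65 | 61.6% | 65.5% |
| 2 | 0.65 | 61.6% | 63.4% |
| 2 | 0.4 | 20.9% | 21.6% |
| 1 | 0.65 | 61.6% | 61.7% |

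With all five real at 0.65, the chance of showing all five is 19% against 44%. With three real, the error among the two null outcomes is 1.9% against 3.5%, both under 5%. In no simulated trial did Bonferroni reject where Holm did not.

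**Which d is plausible.** The only planning effect in the documents is 0.15 against 0.32. Its test statistic at 39 per arm has mean 0.17 / sqrt((0.1275 + 0.2176)/39) = 1.81, which corresponds to d = 1.81/4.416 = 0.41. The d = 0.4 rows are therefore the nearest to anything the plan states.

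**Other family sizes.** If each test alone has 80% power and all effects are real, average power goes from 71% to 76-77% for m = 2 and from 54% to 65-66% for m = 7. If each alone has 42% power (the plan's rates at 39 per arm and alpha 0.05), it goes from 32% to 35-36% for m = 2 and from 18% to 20-22% for m = 7.

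**The case against.** The strongest objection is that both methods are valid and the plan chose one of them. Nothing in the trial is biased or uninterpretable because of Bonferroni. That stands, and it is why this is offered as an improvement only.

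A reader might infer that the plan gives power away for nothing. The documents do not support that, for four reasons.

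- The correction is conditional and the family undefined. There are two arms and one primary variable, drained volume. Tested alone, it is at 0.05 under either method.
- The larger gains need several sizeable effects in one family. No document supports d = 0.65 for any of these outcomes. For surgery, a binary outcome, it would take roughly 32% against 7%, well beyond the plan's 0.32 against 0.15; treating it as a normal statistic is also approximate.
- The five-outcome family is an assumption. It leaves out adverse effects and mortality, and section 2.4 predicts no difference in mortality.
- Bonferroni offers something in return: one fixed threshold per test and simple simultaneous confidence intervals.

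It can also be said that a much larger power question lies elsewhere. At alpha 0.05 the section 3.3 calculation gives 108 per arm, and 39 per arm has about 42% power by the normal approximation. That is correct, but it is a separate matter which neither method addresses.

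What the objection does not remove is that, for significance testing, Holm is at least as good for every family and every dependence structure.

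**Conclusion.** The point holds as a minor, cheap improvement. The mathematical part is certain: same family-wise error, no added assumption, never fewer rejections. The benefit for this trial is uncertain. Across the families and effects examined it runs from essentially zero (one real effect) to about 12 points of average power (seven outcomes, all real, each with 80% power alone). Near the plan's own planning effect, with five outcomes, it is about 4 points if all five are real and under 1 point if two are. All these figures rest on an assumed family, effect sizes and correlation. They do not show that the Bonferroni rule is wrong, or that the primary comparison loses power through it.

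**What to change.** In section 3.7 Statistical Analysis, replace the reference to the Bonferroni correction with wording such as: Holm step-down procedure at family-wise 0.05 (order the m p-values, compare the smallest with 0.05/m, the next with 0.05/(m-1), and so on, stopping at the first that fails). In the same sentence name the outcomes in the family, which fixes m, and say whether the primary outcome is tested outside it at 0.05. Report Holm-adjusted p-values for that family. Make the change before any outcome comparison is run, so that neither the method nor the family can be chosen after seeing p-values.

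The cost is one or two sentences, with no extra patients, data or software; the thresholds can be applied by hand to the SPSS output. The downside is that simultaneous confidence intervals matching Holm are less simple than Bonferroni intervals. The plan does not promise any, so little is lost.

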### 3.8 Estimated cost of study

MAIN ITEM	JUSTIFICATION	Unit	TOTAL (RM)
t-PA (Alteplase) 50mg (Per vial)	Intrapleural fibrinolysis drug (5 vials)	RM 2550.12	RM 12750.60
DNase 2.5mg per ampoules (1 pack contains 6 ampoules of DNase)	Intrapleural fibrinolysis drug (86 ampoules)	RM 190.90	RM 8208.7

Total (RM)		RM 20 959.30
------------	--	--------------

### 3.9 Research ethics

The study will commence upon approval from the Ethics and Research Committee in UKMMC.

#### CHAPTER 4: GANTT CHART

Progression / Timeline	Nov 2022 - Jan 2023	Jan - June 2023	June 2023	June 2025	July-Nov 2025	Nov 2025
Formulating research title and literature review						
Proposal write up and editing						
Proposal presentation and modification						
Proposal submission and ethic committee approval						

Commencement of study and data collection						
Data analysis						
Thesis write up / Dissertation preparation						
Dissertation presentation and submission						

## APPENDIX 1 :

### DRUG ADMINISTRATION OF INTRAPLEURAL t-PA (ALTEPLASE) & DNase (PULMOZYME)

Drugs dosage	Intrapleural t-PA 5mg per dose Intrapleural DNase 5mg (2 ampoules of 2.5mg) per dose at least 6 hrs apart Timing of administration: 8-9 am, 4-5 pm & next day 8-9am.	
Patient undergoing hemodialysis	No dosage adjustment provided. Suggest for heparin free dialysis while receiving t-PA and DNase	
Patient on anticoagulant	No standard guideline. Physician to assess patient's thrombotic risk & bleeding risk and decide if need to withhold anticoagulant.	
		Elimination half life
	Warfarin	20-60 hours
	Rivaroxaban	5-9 hrs ; Elderly: 11-13 hrs; renal impairment: 8.7-9.5 hrs; hepatic impairment: 10.1-10.4 hrs)
	Apixaban	~12 hrs (8-15 hrs)

	Dabigatran	12 -17 hrs; Elderly: 14-17 hrs; Mild-to-moderate renal impairment: 15-18 hrs; Severe renal impairment: 28 hrs
--	------------	---

